**In this study, we show that.**

### **Introduction**

The World Health Organization (WHO) stated that the worldwide prevalence of psychotic disorders is estimated to be around 3 in 1000 individuals with 3.5% of the general population (WHO, 2019). Psychotic disorders affect a person's thoughts, behavior, and emotions which are characterized by symptoms such as delusions, hallucinations, disorganized speech, and behavior. These disorders are linked to a significant loss of psychological wellbeing, which can lead to feelings of hopelessness, helplessness, and despair (Heinze et al., 2018; de Winter et al., 2022).

Patients with psychotic disorders often experience poor psychological wellbeing, which encompasses negative emotions such as anxiety, depression, fear, hopelessness, and despair. The factors contributing to this poor wellbeing are complex and can include biological, environmental, and social causes (Fornells-Ambrojo et al., 2016). Furthermore, symptoms of psychotic disorders, such as delusions, hallucinations, depressed and shifted mood can contribute to negative emotions, which can impact the overall psychological wellbeing of the patient. The prevalence of poor psychological wellbeing among psychotic patients is high, and it can significantly reduce their quality of life, impair their daily functioning, and increase their risk of self-harm and suicide. Adding, psychotic patients often experience a loss of hope, which refers to a state of pessimism and despair where individuals feel their situation is unlikely to improve. (Heinze et al., 2018; Shenoy & Praharaj 2023).

Poor social adjustment is a common challenge experienced by individuals with psychotic disorders. It refers to difficulties in adapting to and functioning in social situations and relationships (Smart et al., 2020). Furthermore, Tee et al., 2020 highlighted the importance of social support and social networks in promoting social functioning and reducing social isolation among individuals with psychotic disorders. Poor social adjustment can significantly impact the lives of individuals with psychotic disorders, reducing their quality of life, impairing their ability to function in daily life, and increasing their risk of relapse and hospitalization (Couture et al., 2019). Therefore, providing complementary interventions to routine care aimed at improving social adjustments and improving levels of hope which enhance psychological wellbeing are essential for the well-being of individuals with psychotic disorders (Kontos et al., 2021).

Complementary interventions, also commonly referred to as complementary and alternative medicine or integrative approaches, can offer several potential benefits for individuals with psychotic disorders. It's important to note that while some complementary interventions may be helpful, they should not be used as a substitute for evidence-based medical treatment. Horticulture therapy as one of complementary therapy is an effective and promising intervention for individuals with psychotic disorders, providing a range of benefits for their physical and mental well-being (Patricia et al., 2017; González et al., 2011; Siu et al., 2020)

Horticulture therapy involves gardening and plant-related activities as a form of therapeutic intervention, enhance patient to be mindful to current environment and promote relaxation which can reduce symptoms such as anxiety, depression, and social isolation, improve cognitive function, and promote overall well-being .With this respect, there is an urgent need to find a sustainable and eco-friendly solution for this complex issue by returned to nature and utilizing the low cost and current resources at the same time to make a signification reduction in the psychotic disorder's symptoms (Gorman, & Anwar, 2022; González et al., 2011; Kontos et al., 2021).

For instance, a systematic review by Van den Berg et al. (2015) found that horticulture therapy had positive effects on social functioning and quality of life in individuals with various mental health conditions. Horticulture therapy is promising therapy in promoting hope, the well-being of individuals with psychotic disorders, providing a low-cost, non-invasive, and engaging therapeutic option (Hernandez, & Garcia, 2022; Lu et al., 2021; Siu et al., 2020).

Horticulture therapy has been found to have positive effects on individuals with psychotic disorders, promoting social interaction, reducing social isolation, and improving cognitive function (González et al., 2011; Hemmati-Sadeghi et al., 2021; Siu et al., 2020; Van den Berg et al., 2015). Effectiveness of horticulture therapy in enhancing well-being, reducing symptoms, and facilitating social adjustment in this population, is (González et al., 2011; Siu et al., 2020; Van den Berg et al., 2015).

The research on horticulture therapy's impact on psychological well-being, hope, and social adjustment among patients with psychotic disorders holds significant importance for both patients and nursing professionals. It suggests that horticulture therapy programs can be a valuable therapeutic option, offering a non-invasive and engaging approach to promoting psychological well-being and social adjustment (González et al., 2011; Siu et al., 2020; Van den Berg et al., 2015). Additionally, by fostering social interaction and reducing isolation, horticulture therapy

provides opportunities for individuals with psychotic disorders to connect with others and establish supportive relationships (González et al., 2011; Siu et al., 2020).

Nurses have a crucial role in implementing and advocating for horticulture therapy programs, facilitating patient engagement, and providing ongoing support throughout the therapeutic process. The research underscores the potential of innovative and effective therapeutic interventions, such as horticulture therapy, to improve patient outcomes and enhance nursing practice (González et al., 2011; Siu et al., 2020; Van den Berg et al., 2015).

**The present study aimed to:**

Assess the impact of Horticultural Therapy Program on Psychological wellbeing, Hope, and Social Adjustment among patients with psychotic disorders.

**Research Hypothesis:**

Patients with psychotic disorders who received Horticultural Therapy exhibited higher psychological wellbeing, Hope, and Social Adjustment than those who didn't receive it.

**Study method& Procedure**

**Research Design:**

A quasi- experimental research design will be followed.

**Setting:**

The research took place at El-Maamoura Hospital for Psychiatric Medicine, which is affiliated with the Ministry of Health and Population. This hospital serves three governorates: Alexandria, Matrouh, and El-Beheira. It consists of a total of 21 wards, providing a combined capacity of 948 beds. Among these wards, 14 are dedicated to psychiatric care, catering to approximately 880 patients with psychotic disorders. Within the psychiatric wards, there are six free wards and four private wards, with two private wards for males and two for females. The private wards accommodate around 130 patients with psychotic disorders at any given time.

In addition to the general wards, the hospital includes specialized units, such as male and female intensive psychiatric care wards, adolescent wards, a psycho-geriatric ward, an addiction center, and an outpatient clinic for psychiatric and substance-dependent patients.

**Administrative steps**

Official written permission from General Secretariat of Mental Health and El-Maamoura Hospital for Psychiatric Medicine will be obtained for conducting the study after taking the ethical approval.

### **Ethical Considerations:**

The necessary formal approval and permission to conduct the study will be obtained from the Research Ethics Committee of the Faculty of Nursing, Alexandria University, Egypt. Patients will be informed about the purpose of the study and an informed written consent will be obtained. Also, they will tell that they have the right to refuse to participate in the study and that their decision will not affect their care. In addition, they will also say that they have the right to withdraw from the study at any time even after starting and that their privacy and confidentiality will be maintained.

### **Participants:**

The G\* Power windows 3.1.9.7 program will be used to estimate the sample size using the following parameters: total sample size around 880, effect size = 0.5,  $\alpha$  err prob=0.05, Power (1- $\beta$  err prob) =0.95, Number of groups=2, Number of measurements=3, Corr among rep measures=0.5. The program estimates a minimum sample size of 54 patients, the researchers decided to recruit 60 patients for the control group and 60 patients for the study group. To be eligible in the study, patients diagnosed with schizophrenia and bipolar disorder with no comorbidity, not in the acute stage, absence of any allergy toward plants, their duration of illness not exceeding 10 years and able to communicate coherently and relevantly as well as can read and write.

A proportionate stratified randomization sample technique from each unit will be obtained using the following formula: Total sample size/ size of the entire population  $\times$  the expected population size of each unit. The required sample size will be selected randomly. Patients of the study group will be randomly subdivided into six groups with ten patients in each group and will receive 8 one-hour group sessions of interventions, in addition to the routine hospital care. The control group will receive routine hospital care only (psychiatric examination, diagnosis, and pharmacotherapy).

A total of 850 participants will be approached, 120 patients will select randomly, 60 for control and study group equal. To ensure that all hospital wards that serve adult patients with psychotic disorders will properly be represented in the study sample, the stratified sampling technique will used through applying the following steps:

- a. The 14 of psychiatric wards will be divided into two strata based on male: female proportion; (8 adult male and 6 adult female wards for psychotic patients).
- b. Considering the male to female wards ratio around (3: 2), random selection of adult psychotic wards will do using simple randomization technique to pick up 50% of these wards (7 wards).
- c. On each randomly selected ward, all patients' medical charts will be screened to identify

patients who met the predetermined inclusion criteria.

d. From all patients who met the predetermined inclusion criteria in the selected ward, one third of them will be picked using simple randomization technique (almost the same proportion used in the decided upon number of subjects. Steps will repeat until the number of decided upon subjects will reached for control and study group 60 patients each.

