#### **Tool I: social and health profile form:**

This form divided into two parts:

- **Part I** is concerned with patients' socio-demographic data such as sex, age, marital status, educational level, working status, and place of residence.
- **Part II** aimed to elicit data related to patient's health such as duration of illness, presence of plant allergy, previous psychiatric treatment, and medications currently prescribed.

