**Implementation of the Horticultural Therapy Program**

On each recruited ward patients will interview individually to establish rapport and to apply tool I (A Socio-demographic and Clinical data Structured Interview Schedule) to elicit their sociodemographic and clinical characteristics. Each patient gets detailed explanations in relation to the aim of the study and objectives of the training and tool I, II, III, and IV. The latter two steps will do for the control group to take base line data and cross matching with study group will be applied.

Egyptian Horticultural Therapy Program will develop by researcher in psychiatric nursing and **botanist** (reference) that included planting, watering, follow up, and harvesting plants. It consisted of eight group sessions; a 30-minute session will be conducted once a week for eight weeks. The first introductory session will concern participants sharing their interest in and experiences with plants, defining the goals of HT about their past horticulture experiences. At the end of the first session, a written plan for every session (time, duration, and setting) will be scheduled individually with each patient. Session conduct by two general group as female group and male group.

The therapist emphasized the use of two plants, one that produces a crop (Cloves) and the other one aromatic and floral plant (Lavender). *Insert Table 1*

Session	General objective:	Steps
Opening session	Emphasizing the general aim of	General information about

I-
	
-planting
 
Empowering self-competency to take care of plant
	
-psychosocial benefit of planting.
 
Name the plants with presentable product of Cloves and Levander.
 
Asking about feeling toward plants and process of planting
 
Give detailed brochure about steps of planting.
 
Providing tool of planting -(seeds, seedlings, soil, pots.....)
 
Give note of schedule about daily expression of emotion

II- Beginning of Hope
	
- Learning and practicing planting
 
- Assuring the understanding
	
- ???????

III- It grows green
	
- Learning and practicing propagation skills.
 
- Reflecting on and sharing thoughts about the vitality of plants.
	
- Expression of patients note

IV- Attention and follow up
	
- Focusing on patients' emotions
 
- Practice the emergency care
	
- Debriefing and expression of patient's emotion
 
- Write note about current

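### The protocol gives a random step for choosing wards, patients and therapy subgroups, but none that assigns a selected patient to the study or control arm

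*Protocol*

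**What the plan says.** All places are in the protocol.

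- Research Design: "A quasi- experimental research design will be followed".
- Participants, arm sizes: "120 patients will select randomly, 60 for control and study group equal".
- Participants, step b, wards: "random selection of adult psychotic wards will do using simple randomization technique to pick up 50% of these wards (7 wards".
- Participants, step d, patients: of those eligible on a chosen ward, "one third of them will be picked using simple randomization technique". The step closes with "Steps will repeat until the number of decided upon subjects will reached for control and study group 60 patients each".
- Participants, therapy subgroups: "Patients of the study group will be randomly subdivided into six groups with ten patients in each group".
- Implementation of the Horticultural Therapy Program: after describing baseline data collection in the control group, the text adds that "cross matching with study group will be applied". It names no variables, ratio or timing.
- Research Hypothesis: patients who received the therapy are expected to score higher on wellbeing, hope and social adjustment than patients who did not.

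**The concern.** The hypothesis is a comparison between arms, so its interpretation depends on how the arms came about. The protocol describes every other selection step and leaves this one out. Assignment is carried out at enrolment, before any analysis, so it belongs in the protocol and is not a detail that a SAP would normally supply.

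Someone following the text could split the 120 at random, place patients in arms by convenience or by judgement, or choose controls to match study patients. These routes do not carry the same risk. With a random split, the arms differ only by chance before the programme starts. With the others, they may differ systematically in ways that nobody measured, and a difference in the scales afterwards would mix that with the effect of the programme.

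**Working it through.** The protocol states no figure on this point to reproduce, so the check is a reading of each sentence that could serve as an assignment rule.

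**1. Count the random steps.**

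| Step | Size | Random method stated? |
|---|---|---|
| Choice of wards | 50% of 14 = 7 | Yes |
| Choice of patients in a ward | one third of those eligible | Yes |
| Study arm into therapy groups | 6 × 10 = 60 | Yes |
| Selected patients into arms | 60 + 60 = 120 | No |

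The arm arithmetic is consistent. Only the last row lacks a method.

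**2. Test each candidate sentence.**

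- "120 patients will select randomly, 60 for control and study group equal": the adverb belongs to the selection of the 120. What follows gives the sizes of the arms. A random split is a possible reading, but it is not stated.
- The proportionate stratified formula in the same section sets how many patients come from each unit. That is sampling, not allocation.
- "Steps will repeat until the number of decided upon subjects will reached for control and study group 60 patients each": this says when to stop picking. It does not say which arm a picked patient enters.
- "Patients of the study group will be randomly subdivided into six groups with ten patients in each group": this starts from a study group that already exists.
- "cross matching with study group will be applied": this may mean that controls are matched to study patients, or only that the two arms are compared at baseline. The text does not decide between them.
- "A quasi- experimental research design will be followed": the label names no method, but it is the usual name for a design without random assignment.

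No other section gives an allocation sequence, concealment, or a unit of assignment.

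**3. What follows if the arms are not random.** Let D be the programme effect and B the difference that the arms would show at follow-up without the programme. The expected difference between arms is D + B. Under random assignment B is 0 in expectation. Otherwise B can be anything, and adjustment removes only the part explained by what was recorded. Tool I records "duration of illness, presence of plant allergy, previous psychiatric treatment, and medications currently prescribed" together with demographic items, and diagnosis is known from the chart screening. Differences in ward environment or in course over time that these items do not capture stay in B. The documents give no estimate of B.

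**The case against.** The strongest reply is that a random split is the natural meaning of loosely written English: one random draw of 120, half to each arm. It adds that a quasi-experimental study need not randomise, so no promise is broken. Baseline scales are taken in both arms and Tool I covers demographics, illness duration, treatment history and medication, so imbalance can be seen and adjusted for. On this view, asking for concealed randomisation replaces the declared design with another.

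Much of this stands. Random assignment may have been intended, and the wordings do not strictly contradict each other. A non-randomised design is legitimate if it is described. But the label and the undefined matching count against the random reading, and even a quasi-experimental design must say how its arms are formed. Adjustment helps only with what was recorded.

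Three stronger readings are tempting, and the documents do not support them.

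- *The arms would be whole wards and unbalanced by sex.* Seven single-sex wards cannot divide equally between two arms, so a reader might infer this. But step d appears to fill both arms from the same wards. Even 3 against 4 wards would not force a sex imbalance, because numbers per ward are not fixed.
- *The study arm cannot be divided into single-sex groups of ten.* This takes the 3:2 in step b as a ratio of patients. It is a ratio of wards, and the protocol fixes no split of patients by sex.
- *A specific inflation of the false-positive rate.* Any such percentage would rest on an assumed bias and would apply to any non-randomised study with 60 per arm. It would not be evidence about this one.

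**Conclusion.** The point holds as a gap in the protocol: the rule that forms the two arms is not stated, and the text permits non-random arms for the only comparison that the hypothesis makes. It should be corrected before patients are assigned.

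It does not show that the arms will be non-random, nor that the protocol contradicts itself. The consequence is conditional: if assignment is not random, unmeasured differences between arms are confounded with the programme effect, and the causal conclusion must be limited accordingly. All 120 patients are affected. The size of any bias is unknown, since the documents give no figure for differences between wards or arms. The conclusion rests on the protocol alone; a SAP may exist, but it would not normally be the place for this step.

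**What to change.** **Preferred.** In Participants, after step d, state that once consent and baseline assessment are complete, the 120 selected patients are assigned 1:1 from a computer-generated list prepared in advance and concealed from those who enrol. Stratify by sex, since the programme section runs sessions separately for women and men. Revise the label under Research Design to match, and say in the programme section what cross matching means. If random assignment was already intended, saying so is enough.

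**If a non-randomised design is kept.** Name the unit of assignment (patient or ward) and how it enters each arm. Say whether cross matching is matching or a baseline comparison, and list its variables. Limit the causal conclusion.

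**Cost.** Stating the rule costs wording. Randomising adds one draw from the list that the sampling steps already build, with no further patients or assessments. Two practical consequences should be accepted openly:

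- The average is 120 / 7 ≈ 17 patients per chosen ward, so 8 or 9 study patients per ward if numbers are roughly even and seven wards suffice. Groups of ten would then draw on more than one ward.
- Patients of both arms may share a ward and exchange material or react to being left out. Step d probably produces this already. The documents give no figure for it, so state possible contamination as a limitation.

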### **Tools:**

The following four tools will used to collect data:

#### **Tool I: social and health profile form:**

This form divided into two parts:

- **Part I** is concerned with patients' socio-demographic data such as sex, age, marital status, educational level, working status, and place of residence.
- **Part II** aimed to elicit data related to patient's health such as duration of illness, presence of plant allergy, previous psychiatric treatment, and medications currently prescribed.

#### **Tool II: The Herth Hope Index (HHI)**

This scale is a self-reported tool designed to measure an individual's sense of hope and optimism (Herth, 1991). It consists of twelve items that are rated on a four-point Likert scale, ranging from "strongly disagree" to "strongly agree,". The HHI has been used in research studies, including those involving individuals with psychotic disorders, such as schizophrenia, to measure hopefulness, reported to be valid and high internal consistency (coefficient  $> 0.90$ ) (Mahmoud, Ali, & Hafez, 2021).

The reliability of the HHI has been demonstrated in various studies, including those involving individuals with psychotic disorders. Similarly, a study published in the International Journal of Mental Health Nursing in 2019, which evaluated the effectiveness of therapeutic horticulture for individuals with clinical depression, reported high internal consistency for the HHI (González et al., 2011).

#### **Tool III : Ryff psychological wellbeing scale (PWBS):**

The Psychological Wellbeing Scale (PWBS) was developed by Ryff in 1989 and modified to 18 items. The PWBS consists of seven-point Likert scales for each of its six subscales, which include autonomy, environmental mastery, personal growth, positive relations with others, purpose in life, and self-acceptance. The scores for each subscale are averaged, with higher mean scores indicating greater psychological wellbeing. Studies of psychotic patients have shown that the PWBS has high internal consistency, with alpha coefficients ranging from 0.78 to 0.88 (Mahmud, Islam, & Sharif, 2022).

